9.1.1. Adverse Events Leading to Withdrawal

A summary of incidence rates (frequencies and percentages) of TEAEs leading to withdrawal of study drug and TEAEs leading to withdrawal of study, by SOC and preferred term will be prepared for the Safety population.

9.1.2. Deaths and Serious Adverse Events

TESAEs will be tabulated by SOC and PT and presented by groups and overall. Fatal AEs will be flagged in the AE listings.

9.2. Local Tolerability Assessments

The investigator's assessment of the application site reaction will be summarized using both categorical methods (number and percentage of subject with each score) as well as continuous methods (e.g., mean, median, etc.). Categorical summaries will be provided for dermal response as well as other effects.

The subject's assessment of the application site reaction will be summarized similarly.

Primary baseline will be used for Cohort 1 Group 1 and OLE baseline for Cohort 2. Overall group will be summarized using Safety baseline.

9.3. Clinical Laboratory Evaluations

Laboratory test results will be summarized descriptively by groups and study visit as both observed values, changes, and percent changes from baseline values for continuous hematology, chemistry, and urinalysis results. Categorical urinalysis results will be summarized using frequencies by groups and study visit.

The number of subjects with clinical laboratory values below, within, or above the normal range by study visit and in relation to baseline will be tabulated for each clinical laboratory analyte (shift table).

Primary baseline will be used for Cohort 1 Group 1 and OLE baseline for Cohort 2. Overall group will be summarized using Safety baseline.

Abnormal laboratory values will be presented in the listings.

9.4. Vital Signs

Descriptive summaries of observed values, changes, and percent changes from baseline will be calculated for systolic blood pressure, diastolic blood pressure, heart rate, height, weight, body mass index, and oral body temperature by group and study visit.

Categorical percent changes in weight (i.e., shifts from baseline) by group will be summarized by the number of subjects who gain or lose $\geq 5\%$ of their baseline body weight during the course of the study, as well as subjects who gain or lose $\geq 10\%$ of their baseline body weight over the course of the study by groups and study visit.

BMI is derived as specified in Section [6.1.7](#). Shift tables for subjects who shift from their baseline BMI category (underweight, normal, overweight, obese) to a different BMI category throughout the course of the study will be provided by groups and study visit.

Shift tables for weight and BMI will also be summarized by intentional and unintentional weight loss (defined from question on vital sign eCRF). Vital signs summaries will use primary baseline for Cohort 1 Group 1 and OLE baseline for Cohort 2. Overall group will be summarized using Safety baseline.

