3.3.2. Oral Roflumilast Tablet

Oral roflumilast (DALIRESP®, DAXAS®) has been approved globally for the treatment of COPD and has been evaluated in nine Phase III/IV randomized double-blind clinical trials ([Wedzicha 2016](#)). Overall, the safety of oral roflumilast has been well established in its targeted population of mostly middle- and upper-aged individuals who currently smoke cigarettes or have smoked them extensively in the past. Adverse events (AEs) reported with roflumilast tablets have been consistent with those expected for oral PDE-4 inhibitors. In a pooled analysis of safety data from 6-month and 1-year clinical trials (N=8630), the most common AEs were diarrhea, weight loss and nausea. Other AEs reported more frequently with roflumilast treatment than with placebo were back pain, influenza, insomnia and decreased appetite ([Michalski 2012](#), [Wedzicha 2016](#)).

In addition to the self-reported cases of weight loss in the 6-month and 1-year oral trials, clinically significant weight loss was also reported in two prospective studies that evaluated weight ([Michalski 2012](#)).

Psychiatric-related AEs were also greater in patients treated with roflumilast tablets (5.9%) compared to those treated with placebo (3.3%). The most common psychiatric-related AEs were insomnia, depression and anxiety. A small number of cases of completed suicide and suicide ideation have been reported in patients taking oral roflumilast in clinical trials and also during post-marketing experience ([Michalski 2012](#)).

The only contraindication to oral roflumilast is usage in patients with moderate to severe liver impairment (Child-Pugh B or C), where systemic levels of roflumilast may become elevated.

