3.1. Overall Design

This is an open-label, single-arm, long-term 52-week safety study of subjects with seborrheic dermatitis. This study will include both male and female subjects 9 years and older. Subjects rolling over from ARQ-154-116 (Cohort 1 Group 2) will not be summarized in the tables and would be listed only.

Cohort 1: This includes subjects of age 9 years or older from ARQ-154-203 and ARQ-154-116 studies and rolled into this extension study on the final visit from previous study. Subjects rolling over from ARQ-154-203 and ARQ-154-116 are separated into groups as indicated below.

Group 1: Subjects rolled over from ARQ-154-203 without gap

Group 2: Subjects rolled over from ARQ-154-116 (listings only and will not appear in summary tables)

Cohort 2: This includes subjects of age 12 years or older who may or may not have participated in a prior ARQ-154 study. The subjects could be either de novo subjects (requiring an IGA of disease severity of at least Moderate [“3”] at Baseline) or subjects who completed an ARQ-154 study before the initiation of this study (any IGA at Day 1 of this

study is allowed). Subjects in Cohort 2 are separated into groups as indicated below:

Group 3: Subjects rolled over from ARQ-154-203 with gap

Group 4: De novo subjects

Subjects will apply study drug once a day for up to 52 weeks. Subjects in both Cohorts cannot have more than 20% BSA affected by disease. All lesions on a subject will be treated including the scalp, face, trunk, and intertriginous areas.

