- **Duration of IGA of 0** = the date of first observation of IGA > 0 - the date of first observation of IGA of 0 and stop treatment. The duration of IGA of 0 for subjects who end treatment in IGA success will be censored at the last disease assessment date. This is for subjects who achieve IGA of 0 and stop the treatment. Subjects who achieve IGA of 0 but never stop treatment will be excluded from the analysis. For subjects who achieve IGA of 0 but stop the treatment later, the duration starts from the date of stop treatment. Only the first IGA of 0 duration will be analyzed.
- **Duration of IGA of 0 or 1** = the date of first observation of IGA > 1-the date of first observation of IGA of 0 or 1 + 1. The duration of IGA of 0 or 1 for subjects who end treatment in IGA of 0 or 1 will be censored at the last disease assessment date. Only the first IGA of 0 or 1 duration will be analyzed.
- **Disease recurrence** = the date of first observation of IGA of 2 or above after achieving IGA of 0 and stop treatment - the date of first observation of IGA of 0 + 1. Only the first disease recurrence will be analyzed.
- **Treatment-free interval** = the date of re-starting study drug due to IGA score above 0 - the date of stop treatment due to attainment of score of IGA of 0 +1, among subjects who achieve a “completely clear” IGA and stop treatment to all lesions. If subjects never re-start study drug after stopping treatment, the treatment-free interval is censored at the end of study date. Only the first treatment-free interval will be analyzed.
- **Weight of IP (g)** = dispensed can weight – returned can weight.
- **BMI (kg/m²)** = (weight in kg)/[(height in cm/100)²]. Day 1 height will be used for BMI derivation upto Week 24. For visits including week 24 through week 36, week 24 height

will be used to derive BMI. Week 52 BMI is derived using the height and weight collected at the same visit. This derivation is applied since height is not collected at all visits.

- **BMI Categories:**

- Underweight: $BMI < 18.5$
- Normal: $18.5 \leq BMI \leq 24.9$
- Overweight: $25.0 \leq BMI \leq 29.9$
- Obese: $BMI \geq 30.0$

- **WI-NRS 4-point reduction** = achievement of a 4-point reduction in WI-NRS pruritus score post-baseline compared to baseline, calculated only for subjects with a pruritus score of ≥ 4 at baseline.
- **Itch-free state** = achievement of in WI-NRS of 0 or 1.

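### The SAP's BMI shift table applies adult cut-offs to minors, and growth attenuates the weight-loss counts in under-18s; tabulate them separately with growth-standardised measures

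*SAP*

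**What the plan says.** **BMI categories.** SAP section 6.1.7 defines four categories by single limits, beginning with "Underweight: $BMI < 18.5". Normal then runs to 24.9, overweight from 25.0 to 29.9, and obese from 30.0. None carries an age or sex condition. BMI uses Day 1 height until Week 24 and Week 24 height through Week 36, with the explanation: "This derivation is applied since height is not collected at all visits".

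**Tables.** SAP section 9.4 plans "Shift tables for subjects who shift from their baseline BMI category (underweight, normal, overweight, obese) to a different BMI category", by group and visit. It also counts subjects who gain or lose at least 5%, and at least 10%, "of their baseline body weight during the course of the study". (Protocol section 7.2.6 uses strict inequalities, more than 5% and more than 10%.) Section 9.4 further gives observed values, change and percent change for height, weight and BMI, and repeats the weight and BMI shifts by whether weight loss was intentional.

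**Population.** Protocol section 5.4.1 admits subjects from age 9. SAP section 3.1 allows age 9 and older in Cohort 1, and says of Cohort 2: "This includes subjects of age 12 years or older who may or may not have participated in a prior ARQ-154 study". Rollovers from ARQ-154-116 (Cohort 1 Group 2, about 10 subjects) appear in listings only.

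**Age.** SAP section 6.1.6 has age bands of 9-11 and 12-17 for selected endpoints, without naming weight or BMI. The one safety subgroup table named, in section 10, is TEAEs by severity.

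**Why weight is watched.** For oral roflumilast, Protocol section 3.3.2 reports that "the most common AEs were diarrhea, weight loss and nausea". Section 3.4.2 lists weight loss among the known effects of oral treatment that the protocol is designed to detect.

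**The concern.** A fixed adult BMI limit does not mean the same thing in a 12-year-old as in an adult, and many minors change in height and weight over 52 weeks. The two categorical weight tables ignore this in different ways. The BMI table sorts minors by limits not meant for them, has no room below its lowest category, and can record growth as a change of category. The percent-weight table measures against a fixed starting weight, so a minor who falls behind expected weight may still show no loss.

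At stake is how far the plan's tables can show a weight effect in the minors of a study whose sole objective is long-term safety. The effect of growth builds with time, so it is largest at the late visits the study was designed to reach. Elsewhere the plan does treat minors separately: PHQ-A and CDI-2 in place of PHQ-8, and PK sampling in adolescents.

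**Working it through.** The plan gives no figure to reproduce; SAP section 3.2 states that the sample size has no power or precision basis. The category limits, thresholds and visits below come from SAP sections 6.1.7, 6.1.4 and 9.4. All heights, weights and growth rates are assumptions.

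**1. Which minors are in the tables.** Cohort 2 starts at 12. Group 2 is excluded from tables. Group 1 formally allows age 9 and older, but SAP sections 9.5 and 9.6 say that its parent study, ARQ-154-203, assessed neither PHQ-A nor CDI-2, which suggests few or no minors enter that way. That is an inference. The tabulated minors are therefore probably mainly Cohort 2 subjects aged 12 to 17.

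**2. BMI categories.** Weight at the lowest limit = 18.5 × (height in m)²:
- 140 cm: 18.5 × 1.96 = 36.3 kg
- 150 cm: 18.5 × 2.25 = 41.6 kg
- 160 cm: 18.5 × 2.56 = 47.4 kg

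Any minor below these weights starts in the lowest category. Two illustrations follow.
- *Floor:* at 145 cm and 36 kg, BMI = 36/1.45² = 17.1. After a 10% loss it is 32.4/1.45² = 15.4. The category does not change.
- *Growth:* from 155 cm and 44 kg to 161 cm and 49 kg, BMI goes from 44/1.55² = 18.3 (underweight) to 49/1.61² = 18.9 (normal).

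The second case was chosen to cross the limit. Growth need not raise BMI: +8% weight with +4% height gives 1.08/1.04² − 1 = −0.1%.

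**3. The 5% loss row.** Let g be expected growth in weight from baseline to the visit and L the shortfall against expected weight. The row is reached when (1 + g)(1 − L) = 0.95, so L = 1 − 0.95/(1 + g). With yearly growth spread evenly, g at week w is yearly growth × w/52:

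| Assumed yearly growth | Week 4 | Week 12 | Week 24 | Week 36 | Week 52 |
|---|---|---|---|---|---|
| 4% | 5.3% | 5.9% | 6.7% | 7.6% | 8.7% |
| 8% | 5.6% | 6.7% | 8.4% | 10.0% | 12.0% |
| 12% | 5.9% | 7.6% | 10.0% | 12.3% | 15.2% |

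For example, at 8% and Week 52, 1 − 0.95/1.08 = 12.0%. With no growth the figure is 5.0% at every visit. For the 10% row at Week 52, L = 1 − 0.90/(1 + g) = 13.5%, 16.7% and 19.6%.

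Conversely, a minor who is 5% below expected weight at Week 52 shows (1 + g) × 0.95 − 1 = −1.2%, +2.6% or +6.4%. The last is counted as a gain of at least 5%.

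Any Group 1 minor previously on active foam is measured from the parent-study baseline. Week 52 is then target day 421, about 60 weeks, and at 8% a year L = 1 − 0.95/(1 + 0.08 × 60/52) = 13.0%.

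**4. Carried-forward height.** At Weeks 12 and 36 the height is 12 weeks old. BMI is overstated by (true height/carried height)² − 1. For growth of 2 to 8 cm a year at 140 to 160 cm this is 0.58% to 2.65%.

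**5. Number affected.** Neither document gives the number of minors. At an assumed 2% to 20% of about 400 tabulated subjects, it would be 8 to 80.

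**The case against.** The strongest reply is that little is lost. The same SAP section summarises height, weight and BMI as continuous values with change by visit, and splits the shift tables by intent. An unintentional 5% loss goes to the medical monitor (Protocol section 6.1.2), and weight loss is a listed ground for considering removal from treatment (Protocol section 5.4.3). Weight loss reported as an AE enters the TEAE tables, which do have age subgroups. The percent-weight table reports exactly what it claims to report, and Protocol section 7.2.6 calls for it. Early visits are barely affected, and the oldest minors may grow little.

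Most of this stands, and it limits the point. A reader might infer that the plan hides weight loss in children aged 9 to 17. The documents do not support that. The loss count is attenuated in one categorical table and BMI is miscategorised in another, while other displays and individual reporting remain. The 9-to-11 age group may be absent from the tables, since Group 2 is listed only. A reader might also infer a known weight effect of the foam; the documents establish it for oral roflumilast.

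The mitigations still do not close the gap. The continuous summaries pool minors with adults and are not adjusted for growth. The split by intent adds no adjustment. The medical-monitor report uses the same fixed baseline. No weight or BMI table by age is committed.

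**Conclusion.** The point holds in a limited form. The BMI shift table misclassifies minors because its limits have no age condition; the floor below 18.5 and the possible upward move with growth follow from the definition itself. The percent-weight table is correct as change from baseline, but it understates shortfall in growing subjects: slightly at Week 4 and, at Week 52, to the extent that 8.7% to 15.2% below expected weight is needed to reach the 5% loss row under assumed growth of 4% to 12% a year.

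The missing age condition is certain. The practical impact is not, because it depends on the number, age and growth of the minors, which the documents do not give. The tables are descriptive and supporting; the primary TEAE and SAE analyses are unaffected. The change is worth making because weight is a stated safety interest and the remedy is cheap.

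**What to change.** In SAP sections 6.1.7 and 9.4:
- Limit the four-category BMI shift table to subjects aged 18 or older at baseline.
- Show the 5% and 10% weight table separately for under 18 and 18 or older, and reconcile its inequalities with Protocol section 7.2.6.
- For under-18s, summarise age- and sex-standardised weight z-score at each clinic visit, and BMI z-score at Day 1, Week 24 and Week 52, with change from baseline. Those are the visits when height is measured, so no height is carried forward.
- Name the growth reference in the SAP, and state how age at each visit is derived.

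The cost is SAP wording and one or two small tables. Age, sex, height and weight are already collected, and no visit or clinical rule changes. The drawback is small numbers in the under-18 tables.

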9.5. PHQ-8

PHQ-8 will be completed by adult subjects and modified PHQ-A will be completed by adolescent subjects of age 12-17 years inclusive. Data for PHQ-8 and Modified PHQ-A will be classified using each subject's total score at a time point into a category based on the following scoring system:

- None – Minimal depression (0 to 4)
- Mild depression (5 to 9)
- Moderate depression (10 to 14)
- Moderately severe depression (15 to 19)
- Severe depression (20 to 24)

Shift tables showing the category of severity at each study visit will be presented by group. As PHQ-A is not assessed in ARQ-154-203 study, only OLE baseline will be used for this summary.

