	
• Treatment-free interval, defined among subjects who achieve a 'completely clear' IGA and stop treatment to all lesions as the time from attainment of a score of 'completely clear' to re-starting IP.
Statistical Considerations:	
Up to approximately 410 subjects total across Cohorts are planned for this study.
 
The sample size will be sufficient to evaluate the long-term safety of ARQ-154 foam 0.3% up to 52 weeks of treatment.
 
Descriptive statistics will be presented for the endpoint and safety data collected in the clinical trial. This includes the number and percentage of subjects for binary endpoints/ categorical data, and mean, SD, median, Q1, Q3, minimum, and maximum for continuous data.
 
Adverse Events
 
For the primary endpoints, the occurrence of treatment-emergent AEs (TEAEs) and the occurrence of Serious Adverse Events (SAEs) will be tabulated by preferred term and system organ class.
 
In addition, summary tables of TEAEs by severity, by relationship to investigational product, and those leading to withdrawal from investigational product will be created.
 
Vital Signs
 
Descriptive statistics will be calculated for vital signs and change from baseline and percent change from baseline in vital signs over time.
 
Clinical Laboratory Results
 
Descriptive statistics of the laboratory parameters will be calculated at each scheduled time point. Change from Baseline and percent change from Baseline will be summarized at each scheduled time point. Shifts from Baseline will be tabulated.
 
Patient Health Questionnaires
 
PHQ-8/PHQ-A/CDI-2 and C-SSRS questionnaires will be completed by the subjects at all study visits. Descriptive statistics will be calculated for the PHQ-8/PHQ-A/CDI-2. The C-SSRS will be analyzed per the Scoring and Data Analysis Guide from the Columbia Lighthouse Project.
 
Descriptive statistics will be presented for the efficacy data collected in the clinical trial for the subjects who enroll in this study and receive at least one day of IP. For the binary endpoints related to IGA, the proportions of subjects achieving each endpoint will be tabulated at each scheduled visit. For subjects who withdraw from study due to lack of efficacy.
 
The duration of response and treatment-free interval will be analyzed using the Kaplan-Meier method.

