7.2. Safety Evaluation

Descriptive statistics will be calculated for safety data and presented by scheduled study visit for quantitative safety data and frequency counts will be compiled for classification of qualitative safety data. Summaries of local tolerability will be presented by scheduled study visit.

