7.2.4. PHQ-8 and Modified PHQ-A

Data for PHQ-8 and Modified PHQ-A will be analyzed by a shift in state of severity using the following scoring system:

- None – Minimal depression (0 to 4)
- Mild depression (5 to 9)
- Moderate depression (10 to 14)
- Moderately severe depression (15 to 19)
- Severe depression (20 to 24)

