- **PHQ-8** = sum of the 8 questions (individual questions scored as Not at all=0, Several days=1, More than half the days=2, and Nearly every day=3; range for score 0 to 24). If more than 1 item is missing the score should not be calculated. If 1 item is missing the score is calculated as (sum of answered items*8)/number of answered items.
- **PHQ-A** = sum of the 8 questions (individual questions scored as Not at all=0, Several days=1, More than half the days=2, and Nearly every day=3, (range for score 0 to 24). If more than 1 item is missing, the score should not be calculated. If 1 item is missing, the score is calculated as (sum of answered items*8)/number of answered items.
- **CDI-2** = total score is calculated as a sum of the 17 questions (individual questions scored as much or most of the time=3, often=2, some of the time=1, Not at all=0; range for score 0 to 51).
 - CDI-2 emotional problem scale is a sum of 9 questions (Q1, Q3-6, Q8, Q10 -12)
 - CDI-2 function problem scale is a sum of 8 questions (Q2, Q7, Q9, Q13-17)
- **Scalpdex score transformation** = Scalpdex is rated on a 1 to 5 scale which will be transformed to 0 to 100 Scale where 1=0; 2=25; 3=50; 4=75; 5=100. This transformed score is used to calculate scale scores.
- **Scalpdex Emotions Scale** = average of (Q2, Q4, Q5, Q6, Q7, Q9, Q10, Q11, Q12, Q14, Q16, Q17, Q19, Q20, Q22) after transforming to 0 to 100 scale as mentioned above.

Q refers to question number. Q19 will be reverse scored i.e., 1=100; 2=75; 3=50; 4=25; 5=0.

- **Scalpdex Symptoms Scale** = average of (Q1, Q3, Q8) after transforming to 0 to 100 scale as mentioned above. Q refers to question number.
- **Scalpdex Functioning Scale** = average of (Q13, Q15, Q18, Q21, Q23) after transforming to 0 to 100 scale as mentioned above. Q refers to question number.
- **Scalpdex Total Score** = calculated as mean of all the 23 scalpdex questions using the transformed scale of 0 to 100. Q19 will be reverse scored i.e., 1=100; 2=75; 3=50; 4=25; 5=0 while calculating the mean. Q refers to question number.
- **Total % BSA (body surface area)** = sum of coverage areas of head, limbs, upper limbs, and lower limbs.
- **Change from baseline** = value at current time point – value at baseline. This is derived separately for primary baseline and OLE baseline.
- **Percent change from baseline** = (value at current time point – value at baseline)/value at baseline. This is derived separately for primary baseline and OLE baseline.

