9.6. CDI-2

Parents/caregivers will complete the CDI-2 for subjects belonging to 9-11 years of age inclusive. For CDI-2, descriptive summaries of observed values, changes and percent changes from baseline will be calculated for the total score and the 2 scales emotional problems and functional problems by groups and study visit.

As CDI-2 is not assessed in ARQ-154-203 study, only OLE baseline will be used for this summary.

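### PHQ-8 and PHQ-A totals are reported only as shifts between five severity bands, so within-band change is lost and small general drifts are blunted; the protocol sections on this conflict and the choice is not recorded

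*SAP*

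**What the plan says.** SAP 6.1.7 derives PHQ-8 and PHQ-A as sums of eight items, range 0 to 24. SAP 9.5 then sorts each total into five bands (0–4, 5–9, 10–14, 15–19, 20–24) and specifies "Shift tables showing the category of severity at each study visit will be presented by group", using the OLE baseline. It names no mean, median or change in score.

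The protocol says two things:

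- Section 7.2.4, the part specific to these questionnaires, reads: "Data for PHQ-8 and Modified PHQ-A will be analyzed by a shift in state of severity using the following scoring system". The bands are the same as in the SAP.
- The synopsis reads: "Descriptive statistics will be calculated for the PHQ-8/PHQ-A/CDI-2". It explains descriptive statistics as counts and percentages for categorical data, and "mean, SD, median, Q1, Q3, minimum, and maximum for continuous data". Section 7.2 adds: "Descriptive statistics will be calculated for safety data and presented by scheduled study visit for quantitative safety data".

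For the third mood instrument, covered by the same synopsis sentence, SAP 9.6 reads: "For CDI-2, descriptive summaries of observed values, changes and percent changes from baseline will be calculated for the total score". SAP section 10 lists five changes from the planned analysis, none of them about PHQ-8 or PHQ-A. SAP 6.1.8 keeps data that are not analysed under the plan out of tables and graphs, in the CDISC datasets only.

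**The concern.** Protocol 3.3.2 reports psychiatric adverse events in 5.9% of patients on oral roflumilast against 3.3% on placebo, with depression among the commonest. Protocol 4.2.1 lists PHQ-8 and PHQ-A among the measures by which safety is monitored. Both questionnaires give a numeric score, and the only planned display discards most of its detail.

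The loss falls where subjects are likely to be. Cohort 2 entry is capped at a score of about 10, so those subjects start almost wholly in the two lowest bands. (Exclusion 16 in Protocol 5.4.2 excludes 10 itself; the synopsis and Protocol 6.1.4 and 6.1.5 exclude only scores above 10. These passages need reconciling.) Each band is five points wide, so a worsening of up to four points can stay inside one. A report could then describe little or no shift while the average score had moved a little, and its reader would have no table in which to check.

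**Working it through.** **Comparison within the SAP.** The SAP states no figure on this point, so there is none to reproduce. The planned displays of comparable safety measures are:

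| Measure | Continuous summary | Category or shift table |
|---|---|---|
| Local tolerability (9.2) | yes | yes |
| Laboratory values (9.3) | yes | yes |
| Weight and BMI (9.4) | yes | yes |
| PHQ-8, PHQ-A (9.5) | **no** | yes |
| CDI-2 (9.6) | yes | no |

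The synopsis also names descriptive statistics and shifts as separate items for laboratory results, which suggests that a shift table alone was not what it meant by descriptive statistics.

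**Individual change.** A move from 0 to 4 or from 5 to 9 is +4 points and no change of band.

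**A uniform rise.** Share of subjects who change band if every score rises by the same amount, for assumed baselines on 0–9 (the documents give no distribution):

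| Assumed baseline | +1 | +2 | +3 | +4 |
|---|---|---|---|---|
| All at 0 | 0% | 0% | 0% | 0% |
| Geometric, mean 1 | 3.2% | 9.7% | 22.6% | 48.4% |
| Poisson, mean 1 | 1.5% | 7.7% | 26.1% | 62.9% |
| Poisson, mean 2 | 9.0% | 27.2% | 54.6% | 82.9% |
| Uniform 0–9 | 20% | 40% | 60% | 80% |

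Of 400 subjects, a 2-point rise moves between 0 and 0.40 × 400 = 160 up a band. The result depends on how close subjects sit to a cut-off.

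**A small drift with ordinary fluctuation.** Assumptions: 400 subjects (the approximate number in the tables, SAP 4.2); each subject's expected score λ is Gamma with shape 1.5 and mean 1.5, 2 or 2.5; baseline is Poisson(λ), kept if below 10; follow-up is Poisson(λ + a) or Poisson(λ × c). The mean change is judged by a one-sample t test and the net band shift by a sign test, both two-sided at 5% and counted only if worsening. There were 1,500 simulations per scenario, repeated independently. Ranges cover the three means and the repeat runs.

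| Drift | Mean change | Net band shift |
|---|---|---|
| +0.3 point | 91–94% | 21–49% |
| +0.5 point | about 100% | 53–82% |
| +0.75 point | about 100% | 89–99% |
| +1 point | about 100% | 99–100% |
| ×1.15 | 72–98% | 34–81% |

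At +1 point, average upward against downward band changes are 46 v 13, 62 v 19 and 75 v 24 subjects for the three means, an imbalance that a reader of the shift table would see.

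With no drift at all, worsening was declared in 3–11% of runs from the score and 2–9% from the bands. The entry cap removes high baselines, so later scores rise slightly by regression to the mean.

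**Precision after the fix.** The 95% half-width of a mean change is 1.96 × SD / √400. For an assumed SD of 2, 3 or 4 it is 1.96 × 2/20 = 0.20, 1.96 × 3/20 = 0.29 or 1.96 × 4/20 = 0.39 points, at visits with near-complete data.

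**A related gap.** SAP 6.1.7 prorates: "If 1 item is missing the score is calculated as (sum of answered items*8)/number of answered items". With seven items answered, sums of 4, 8, 13 and 17 become 4 × 8/7 = 4.57, 9.14, 14.86 and 19.43, which fall in no band.

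**The case against.** The strongest reply is that SAP 9.5 does what the most specific protocol text asks. Protocol 7.2.4 is the only statistical section devoted to these questionnaires, and it names the severity shift and nothing else. The synopsis says descriptive statistics without saying score, and a table of counts is a descriptive statistic. This stands to the extent that a reader should not infer that the SAP dropped something the protocol plainly promised. The protocol conflicts with itself, and reading the synopsis as score summaries is an inference from the total being numeric. It is a sound inference, since the SAP reads the same sentence that way for the CDI-2, but the conflict remains unrecorded on either view.

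A second tempting inference is that a general worsening of mood cannot be seen in the planned tables. The working does not support it: under the same model a rise of 0.75 to 1 point shows clearly in the bands. The loss is confined to within-band changes and to drifts of roughly half a point or less, and nothing in the documents says that drifts so small matter clinically.

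It is also fair to say that other safeguards exist. Psychiatric events enter the TEAE tables, the C-SSRS is tabulated by visit, and a score of 15 or more prompts referral. The two planned primary analyses are TEAEs and SAEs, not the questionnaires. SAP 6.1.2 plans no inferential analysis, so the power figures compare tests that will not be run. These points limit the importance of the gap without closing it.

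**Conclusion.** The point holds as a gap in reporting and an unreconciled conflict between protocol sections. SAP 9.5 follows Protocol 7.2.4 but leaves out the descriptive statistics that the synopsis and Protocol 7.2 call for, and section 10 is silent. That within-band changes vanish from the planned tables follows directly from the bands and needs no assumption. The size of the blunting does rest on assumptions: for a 0.3-point general rise, about 92% against 21–49%, with the gap largely closed by 0.75 point. It depends on the gamma-Poisson model, the low assumed means and 400 evaluable subjects, and it describes visibility rather than a planned test. The change is worth making because it is nearly free, but the gap does not undermine the study's primary safety analyses.

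**What to change.** In SAP 9.5, beside the shift tables, add by-visit n, mean, SD, median, Q1, Q3, minimum and maximum of the PHQ-8 and PHQ-A total scores and of their change from OLE baseline, by group and overall. Reconcile Protocol 7.2.4 with the synopsis and 7.2; if bands alone are intended, state that in SAP section 10 with the reason. Add a rounding rule for prorated totals before banding. A 95% confidence interval for the mean change is optional, since no passage promises one for safety data.

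The cost is SAP wording and one standard table per questionnaire, with no new data because the totals are already derived. The one downside is interpretive: in a single-arm study with a capped entry score, a slight mean rise may partly be regression to the mean. A footnote to the table should say so.
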